Overall, data collection and intervention in the HoMBRES study presents minimal risks for participants. All of the steps that may be taken to protect the well-being of participants or their family members deemed to be in danger will be described fully to all participants and we will do everything possible to minimize harm to the youth, family or any of its members. The following are possible risks for the participants divided by the study's aims:

Aim 1: During the focus group sessions, participants might reveal highly sensitive information regarding their substance use, sexual behavior, and HIV status; there is a potential risk for breach of privacy and confidentiality regarding these sensitive topics. There is also a risk that some questions may distress the participants. In order to prevent those risks, all participants will be briefed on the issues of confidentiality. Participants will be asked to avoid using their names or naming others and will be asked to maintain the confidentiality of other focus group members. Identifying information will be redacted from transcriptions.

Page 14 of 23 Revised: March 23, 2020

IRB Study Number: Version HoMBRES de Famlia (HoMBRES) #1

Aim 2: No side serious side effects have been noted in the current literature in association with the behavioral questionnaires, interviews, and interventions used in this study, although, as with many assessment batteries, some people may experience mild fatigue or momentary concern about their ability to do well. Although there are no specific questions regarding abuse and neglect of minors or elderlies in the baseline or posttest assessments, there is a risk that participants disclose abuse and other reportable behavior during the assessments or during the interventions. Interviewers will be trained to identify cases of child and elderly abuse (sexual, physical and emotional).

Training will include providing them with a battery of the appropriate questions to ask participants when they report physical punishments, negligence, or sexual abuse. Participants will be reassured that their confidentiality is safe and will be informed that due to federal regulations and Florida statues we are mandated reporters. Interviewers and facilitators are informed also that an incident report needs to be filed within 48 hours.

There is a risk that some of the questions may distress the participants. Adult participants will be asked to provide information about highly sensitive topics such as substance use, sexual behavior, and HIV status. The measures with sexual or substance use questions completed by the youth are gated so that children to limit their exposure to sensitive topics.

During the intervention participant may feel shy or may not feel comfortable talking about certain taboo issues. Additionally, by participating in this research project, participants may become aware of or sensitized to their HIV risks, family violence, risk for a substance use disorder or other health risks. In order to decrease feelings of comfort, participants will be told to speak in a third person.

Providing incentives to participants may inappropriately persuade them to participate in research— pressure that may meet criteria for coercive recruitment, especially because most of those who will participate in the proposed Research Project are persons of very low income.

There is a potential risk for a breach in data security that may infringe on the participant's privacy and confidentiality regarding these sensitive topics. As an NIH sponsored study, the study will automatically be issued a Certificate of Confidentiality. Participants will be made aware that there could be a breach of confidentiality by other participants who might be aware of their participation in the study, given the sampling methodology. However, they will be assured that no data will be linked to their personal information.

Aim 3: The specific procedures for Aim 3 are to be determined

16) Potential Benefits to Subjects*

Aim 1: There are no direct benefits to participant, however participants may occasionally experience a sense of relief or satisfaction discussing barriers that they face in the community.

Aim 2: Benefit participants may receive is referral to services as needed. Participants randomized to the HoMBRES intervention may increase their skills of communicating with their adolescent sons and their knowledge about HIV, substance abuse and domestic violence. Participants randomized to the control intervention may increase their knowledge about health promotion and diabetes prevention.

Page 15 of 23 Revised: March 23, 2020

IRB Study Number:

Version HoMBRES de Famlia (HoMBRES) #1

Aim 3: We do not anticipate direct benefits to participants; however, the community at large may benefit from learning about an intervention for Latino parents that may help men and their sons. Participants will be able to share the results of the intervention with other members of their community and advocate for similar programs from local agencies.

17) Vulnerable Populations*

The youth (ages 11-17) who will participate in this study will be required to have their parent/legal guardian consent to participate and additionally will meet the regulatory requirements described in the HHS regulations, Subpart D. All the consent and assent forms will be submitted to the UM IRB for review and approval. All the adolescents will sign an IRB approved assent form before participation.

The proposed study aims at increasing education and HIV prevention skills among adult men and their adolescent sons, therefore, including youth in the assessment portion is critical for testing the effectiveness of the study.

The intervention HoMBRES was developed for farm working men, a socioeconomically vulnerable population, and therefore the researchers will take all the necessary precautions to ensure confidentiality and avoid coercive approaches. The entire research team has conducted various NIH funded studies and a couple of interventions for this vulnerable high-risk minority population.

Participants will be explained the consent and assent forms in order to ensure that they understand the protocol and will be encouraged to ask guestions.

Aim 2: Participants will be encouraged to ask questions during the interventions and will be asked to provide feedback regarding their experience as well as evaluating the sessions. Sessions will be randomly supervised for quality control during the duration of aim 2.

18) Multi-Site Research* NA

19) Community-Based Participatory Research*

Researchers will be working with various community organizations such as the Farm Workers Association and the Coalition of Florida Farmworkers Organization (COFFO) to recruit and facilitate interventions. These community partners will help us recruit participants for the focus groups which will guide the adaptation of the intervention

Partners from the community will be asked to provide feedback about the intervention during the CAB meetings.

20) Sharing of Results with Subjects*

Under Aim 3, dissemination of the study findings will be accomplished in close collaboration with the Community Engagement and Dissemination Core of CLaRO (parent NIH contract for this study).

Page 16 of 23 Revised: March 23, 2020

IRB Study Number: Version HoMBRES de Famlia (HoMBRES) #1

Strategies for providing relevant information to the LSFW community: Under Aim 3 dissemination strategies will be performed in areas where LSFWs gather, socialize, and celebrate. In MDC, this includes local flea markets, recreational parks, Latino festivals, health fairs, and places. Dissemination activities will include: (a) Presentations to community stakeholders and service providers involved in addressing substance abuse, family violence, and HIV/AIDS in the local community, and (b) Distributing information to the local community via informational booths at local health fairs and ethnic festivals.

21) Setting

Procedures for Aims 1 and Aims 2 will be provided in private community settings including the COFFO offices as well as the Everglades Community Center and Redland farm camp community center or other locations in the urban, semi-rural areas of Homestead, Naranja and Florida City or other locations within walking distance or short drive of participants homes. During the COVID-19 Pandemic, procedures of Aims 2 will be conducted remotely as described above. Once dyads are interviewed, they will be sent a private link with the video sessions based on the group randomization. This approach will help us avoid delays between recruitment, randomization and intervention delivery. Interventions will be facilitated via a secured link. The webinar style video will be solely available to participants using a private link (ie. Zoom, youtube, powerpoint and other venues available to the participants). These venues can provide privacy and confidentiality.

Incentives for participation will be delivered by money order, electronic cash deposits or payments such as Zelle or another electronic platform preferred by participants. It should be noted that participants in this study are of very limited financial means and may not all have access to platforms used at UM (e.g., Zoom), furthermore, we are trying to use means of communication that participants are accustomed to. We will have to assess their technology and will proceed accordingly, using the UM platforms as first line, but may need to use other means of communication and transmission as per participant access.

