Aim 1—Participants in the Community Assessment will be recruited from the community using word of mouth, fliers, and outreach in the community. Focus groups will be facilitated with adult men, adolescents (13-17 years old), and service providers and community leaders, from the community. Criteria for participating in the focus groups are: 1) being a farm worker (or adolescent child of a farm worker) or living in a farm working community or working with the farm working community or being a leader within the community. 2) Speaking and Understanding English or Spanish

Aim 2 - In order to participate in the randomized clinical trial (RCT) intervention - Adult father and son (11-17 years old) dyads, living or working in the farm industry, sales, construction, truck industry, landscaping, self -employment or other work industry or living in the urban areas or semi-rural areas of Miami-Dade such as Homestead, Naranja and Florida City will be eligible to participate in the Research Project.

Prisoners are excluded. Inclusion criteria for RCT participants are shown in Table 1

Table 1. Inclusion Criteria										
Criteria	Inclusion									
	Fathers	Sons								
Age	18 yrs. of age and over	11 to 17 yrs. of age								
Language	Ability to speak and understand Spanish	Ability to speak and understand English or Spanish								
Community residency	Living in the urban or semi-rural areas of Miami Dade such as Homestead, Naranja or Florida City who will remain in area for 6 months or working in the work industries described below or	Who will remain in area for 6 months								
Jobs	Working in the farm industry, nurseries, sales, construction, truck industry, landscaping, self-employed or other work industry. Unemployed fathers are also eligible.									

Page 5 of 23 Revised: March 23, 2020

IRB Study Number:

Version HoMBRES de Famlia (HoMBRES) #1

Consent Able to understand & provide Able to understand & provide

assent and has parental consent consent

Dyad

Be considered a father/father Preferably the youngest eligible of sons 2

figure to participate 1, 2

1. In cases where men have more than one son that meets the inclusion criteria, attempts will be made to recruit the youngest son, which will allow prevention measures as early as possible.

2. In cases where the adult male is not the legal guardian, written consent from the child's legal guardian will be required in addition to assent from the adolescent.

6) Number of Subjects*

Aim 1

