and control group prior to initiating the intervention followed by a 6month follow-up assessment. During the time of social distancing data (for baseline or follow-up assessments) will be collected via telephone calls, FaceTime application, WhatsApp or other remote alternative venues. When CDC recommends that social distancing is no longer necessary, consenting and interviewing may be done by phone or face to face as per participant request. Survey data will be collected utilizing Apple iPad tablet computers and REDCap (Research Electronic Data Capture: survey and data management software). Pre- and post-test for the fathers will be collected using an interviewer administered assessment. Interviews are culturally congruent with our target population—given that some Latinos value personalismo, a cultural feature that values cordial interactions and interpersonal engagement. Interviewer-administered assessments will help mitigate any issues related to poor literacy. The interview with the adolescents will also be remotely administered at baseline and 6 months follow up, using a REDCap link sent to the participants accessible on their phones, computers, tablets or IPads or by telephone. Study staff will be available via telephone to assist adolescents in completing the assessment. Survey administration will take approximately 1 to 2 hours for the fathers and 1 to 1.5 hours for the youth.

Measures:

The following table includes a list of the measures that will be utilized during the baseline and the 6-month follow up of the study:

Table 1. HoMBRES Measures

Page 10 of 23 Revised: March 23, 2020

IRB Study Number:

Version HoMBRES de Famlia (HoMBRES) #1

 Culture-Related Risk/Pro Tailoring of Interventions 							
Cultural Values	Cultural Values Mexican American Cultural Values Scale						
Gender Roles	Gender Roles Machismo and Caballerismo Scale F						
Culture-Related Stress	Culture-Related Stress Hispanic Stress Inventory 2 Hispanic F						
 Risk/Protective Factors th 							
Intervention							
Health Literacy	Health Literacy Screening Questionnaire	F					
HIV Knowledge	HoMBRES Brief HIV Knowledge	F					
	Questionnaire						
Self-efficacy	Self-Efficacy for HIV Scale	F					
Attitudes about Sex	Measure of Sexual Attitudes and Behavior	FY					
Parent-Child Relationship	Family Connectedness Scale	FY					
Family Functioning	Family Environment Scale Parenting	FY					
Parental Monitoring;	Practices Scale	FY					
Parent-Child							

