Adverse Events and Serious Adverse Events (AE and SAE): The Project Lead and protocol PI will be responsible for monitoring and reporting and comply with the reporting requirements of the IR B and NIMHD. The Data and Safety Monitoring plan will have required reports will include any adverse events as well as the results of analysis conducted. The PI and Project Lead will ensure that any AE or SAE are timely reported to the IRB.

During the study implementation, we foresee that they may be certain events with the families such as: 1) domestic violence; 2) work contract was terminated and participant has to move to another city; 3) entire family is moving to another estate; 4) father moved out of the home; 4) father was kicked out of home.

Among the Serious adverse events (SAE) we may encounter: 1) physical abuse with partners and adolescents, 2) hospitalization, 3) substance abuse. All assessments conducted by the study's interviewers are opportunities for identifying adverse events if reported by the participant and/or a family member. The educators will be trained to identify AEs and SAEs at session of the intervention and at each interview or assessment points. Additionally, anytime during the study, a participant or his/her family member may report an AE/SAE to their group facilitators/educators. These events will be identified, classified as serious or not, and will be handled in the same manner as AEs/SAEs during the formal assessments.

Study personnel (including peer advocates) will be trained to identify adverse events, and categorize serious adverse events, based on direct reporting during sessions. Upon identification of an adverse event, the team member should notify the study coordinator who will assess the event for seriousness to guarantee that appropriate care and reporting occur within approximately 24 hours. As soon as an adverse event is identified either by querying or direct report, the event will be recorded in the AE log. In addition, the Project Lead ([name]) or Co-Project Lead ([name]) or Project Coordinator ([name]) will be notified of any and all AEs. In both treatment conditions, action may be taken by the peer advocate to respond to non-serious events (e.g., referral to counselor, community program, local agency or hospital). The

Page 13 of 23 Revised: March 23, 2020

IRB Study Number: Version HoMBRES de Famlia (HoMBRES) #1

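### Table 1 lets a working father qualify without the six-month stay condition that every son must meet, so fathers who already plan to leave before the only efficacy follow-up can be enrolled

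*Combined protocol and SAP*

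**What the plan says.** The inclusion criteria are in Table 1 of section 5 of the combined protocol and SAP. This is not the measures table in section 10, which is also numbered 1.

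- **Fathers, community residency.** After naming the areas of residence, the cell continues: "who will remain in area for 6 months or working in the work industries described below or".
- **Fathers, jobs.** The row lists several industries and ends: "landscaping, self-employed or other work industry. Unemployed fathers are also eligible".
- **Sons, community residency.** The cell holds one condition with no alternative: "who will remain in area for 6 months".
- **Aim 2 text above the table.** It lists kinds of work and then adds "or living in the urban areas or semi-rural areas of Miami-Dade such as Homestead, Naranja and Florida City will be eligible". It contains no six-month condition.

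Section 10 (Assessments) sets baseline data collection in the intervention group "and control group prior to initiating the intervention followed by a 6month follow-up assessment". The 2-3 month telephone contact is a short set of questions to fathers and not an efficacy assessment. Section 13 lists foreseen events during the study, among them that a "work contract was terminated and participant has to move to another city".

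**The concern.** The six-month condition matches the time to follow-up, so its evident purpose is to have both members of the dyad in place for that assessment. In the fathers' cell it qualifies only the living-in-area branch. The working branch, in the same cell, carries no such condition. Sons are held to it without exception, and no reason is given for the difference.

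The asymmetry falls on the member who matters most for several outcomes. Section 10 says that the program is solely parent-based and that sons only complete assessments. The SAVA block of the measures table marks the Timeline Follow-back, PhenX Sexual Risk Behavior and PHQ9 as father-only. Section 12 models outcomes at follow-up with adjustment for baseline and, in the text reviewed, states no method for missing follow-up data. A father not assessed at six months has no outcome on those three measures.

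The protocol does ask fathers whether they plan to move, but at the 2-3 month call. That is after randomization, when eligibility can no longer act on the answer.

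**Working it through.** **Eligibility logic.** The plan states no figure on this point to reproduce, so the check is one of logic. Describe a father by three yes/no facts: L, he lives in the area; R, he will remain six months; W, he is working (no = unemployed). That gives 2 × 2 × 2 = 8 profiles, 4 of them with R = no.

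- *Literal reading*: the trailing *or* joins the residency cell to the Jobs row, which admits any industry and unemployed men. Rule: (L and R) or W or (W or not W).
- *Narrow reading*: the sentence "Unemployed fathers are also eligible" only waives the Jobs row, and unemployed men must still meet residency. Rule: (L and R) or W.
- *Separate condition*: R and (L or W).

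| L | R | W | Literal | Narrow | Separate |
|---|---|---|---|---|---|
| yes | yes | yes | in | in | in |
| yes | yes | no | in | in | in |
| yes | no | yes | in | in | out |
| yes | no | no | in | out | out |
| no | yes | yes | in | in | in |
| no | yes | no | in | out | out |
| no | no | yes | in | in | out |
| no | no | no | in | out | out |
| **Eligible** | | | 8 of 8 | 5 of 8 | 3 of 8 |
| **Eligible with R = no** | | | 4 of 4 | 2 of 4 | 0 of 4 |

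On both readings of the current text, each working profile with R = no is eligible. The readings differ only for unemployed men. If unemployment also counts as meeting the job alternative under the separate condition, 4 of 8 profiles are eligible, still none with R = no.

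**Illustration of what lost fathers would cost.** From section 6: 160 dyads, hence 160 fathers. Assumed, because not stated: 1:1 allocation (80 per arm), two-sided 5% alpha, 80% power, no clustering, no baseline adjustment, and the loss rates themselves.

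Detectable difference = (1.960 + 0.842) × √(2/n) = 2.802 × √(2/n) SD, with n fathers per arm. Power at 0.443 SD = Φ(0.443 × √(n/2) − 1.960).

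| Loss | n per arm | Detectable difference (SD) | Power at 0.443 SD |
|---|---|---|---|
| 0% | 80 | 0.443 | 0.80 |
| 10% | 72 | 0.467 | 0.757 |
| 20% | 64 | 0.495 | 0.707 |
| 30% | 56 | 0.529 | 0.650 |

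The losses are total attrition from any cause. None of the documents' figures says what share, if any, would come from this wording.

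**The case against.** The strongest reply is that this is loose drafting with little practical effect. Most of its parts have force.

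- **The sons' rule is a partial safeguard.** Enrolment is by dyad, so a family that plans to move together is screened out through the son. This stands. It narrows the gap to fathers who plan to leave without the son, a group that can exist because father figures and men who are not legal guardians are eligible.
- **Leaving the area is not loss to follow-up.** Assessments are remote during social distancing. Afterwards, "consenting and interviewing may be done by phone or face to face as per participant request". The sessions are remote during distancing and possibly beyond, and section 10 lists a locator form, corroborative contacts, up to monthly calls and online searches. This stands. A reader might infer that every departing father is a missing outcome, and the documents do not support that.
- **Many of the moves in section 13 are unplanned**, such as a terminated contract or a father put out of the home. This stands. A screening question cannot catch them, and leaving the household is not the same as leaving the area.
- **Fathers are not the only source of data on substance use and sexual risk.** Section 15 refers to youth measures with such questions, and the sexual attitudes and behavior measure is given to both members. This stands. Only the three named instruments are father-only.
- **The criteria were broadened on purpose** (section 4), and a further condition costs some representativeness. That is a fair trade-off to weigh, but it does not explain why sons are bound and working fathers are not.

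The reply does not remove the core point. The bypass for working fathers lies within one cell, so it does not depend on how the table rows are joined.

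**Conclusion.** The point holds for working fathers on either reading: as written, the six-month condition excludes none of them. A reader might go further and say that it applies to no father at all. That follows only if the trailing *or* is carried into the Jobs row. On the narrow reading it still binds unemployed fathers, so the stronger statement is the literal reading and not an established fact.

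The consequence is that fathers already known at screening to be leaving without their sons can be enrolled before the only efficacy follow-up. How many there would be, and how many would be unreachable by phone, cannot be derived from the documents. The range of 0.44 to 0.53 SD shows what general loss of fathers would cost under the stated assumptions and must not be read as the effect of this wording. Nor do the documents show that a departing father ends contact with his son and so dilutes the effect, since no section requires the two to live together.

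This is a modest defect of unquantified size. It is worth correcting because the present text lets screeners apply different rules and the correction is cheap.

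**What to change.** Take the six-month condition out of the *or* chain and give it its own row in Table 1 for both members: father and son each expect to remain in the area through the 6-month follow-up. Keep residence and job as alternatives for fathers, state explicitly how unemployed fathers qualify, and bring the Aim 2 text above the table into line. If the sponsor means to accept fathers who plan to leave, the protocol should say so and explain why sons are treated differently.

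The cost is one table row and a sentence of text in the next amendment, plus one screening question. A few fathers who already plan to leave would be screened out. Unplanned moves would not be prevented and remain a matter for the retention steps.
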